3.4.2.2 Secondary subjects - Patients

- 1) Premature birth: <28 weeks completed gestation
- 2) Cyanotic congenital heart disease
- 3) Pulmonary hypertension
- 4) Home oxygen or positive pressure ventilation requirement
- 5) Tracheostomy
- 6) Neuromuscular disease
- 7) Immunodeficiency
- 8) Cancer
- 9) Historical, current, or suspected diagnosis of heart failure, myocarditis, or arrhythmia
- 10) Historical, current, or suspected diagnosis of COVID-19

Subjects that do not meet all of the enrollment criteria may not be enrolled. Any violations of these criteria must be reported in accordance with IRB Policies and Procedures.

4 STUDY PROCEDURES

4.1 Pre-intervention period

- Implementation champions identified, local teams formed
- Local team members will meet with leadership on each potential unit; unit leadership will be given the opportunity to opt their unit out of the study for any reason.
- Implementation champions & teams perform educational outreach sessions on participating units
 - describing current guidelines
 - summarizing the evidence behind the guidelines
 - discussing potential alternatives to continuous pulse oximetry monitoring for patients in whom guidelines do not advise continuous pulse oximetry
- Distribution/dissemination of educational materials (e.g. slide presentations, posters, flyers, videos) to hospital staff working on study units focused on the bullet points above
 - materials collaboratively developed by the CHOP team and local implementation teams, with site-specific tailoring by the local implementation teams

4.2 Intervention period

- Implementation teams will conduct data collection rounds and supplemental chart review (see Section 5) to determine continuous pulse oximetry status on bronchiolitis patients not receiving supplemental oxygen or room air flow, targeting data collection at least twice per week in order to acquire sufficient data for audit and feedback intervention.
- If any hospital staff responsible for the care of the patient are present and available on the unit, the data collector may perform real-time inquiry if feasible, briefly asking about the indications for monitoring individual patients, which will be documented in the study database as field notes without documenting any of the hospital staff member's identifiers.
- On a weekly basis, the data will be summarized in a dashboard and the dashboard along with the raw data will be returned to the site PI.
- Local implementation team will then share that data in electronic and in-person settings appropriate and tailored to each site (e.g. email, safety huddles,^{24,25} staff meetings, rounds, staff messages in electronic health record systems) with key clinician stakeholders who order or manage continuous pulse oximetry monitoring for bronchiolitis patients. Data will be contextualized with (a) the hospital's prior performance, (b) other hospitals' prior performance, (c) the current performance of other units in the same hospital, (d) the current performance of other units in other hospitals.
- Additional educational materials will be distributed and additional education/outreach sessions will be held by the local implementation team at a frequency determined by the site PI depending on local pulse oximetry use rates.

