5 STUDY EVALUATIONS AND MEASUREMENTS

5.1 Overview

Data collection will be operationalized at sites during periodic in-person observational "rounds" during the intervention period. During a data collection round, site investigators will first identify all

patients currently admitted to their hospital's non-ICU pediatric wards with bronchiolitis by reviewing the census of each unit that cares for children with bronchiolitis and examining the charts of patients meeting age criteria to determine if they are eligible. They will then walk to the bedside of each eligible infant with bronchiolitis to confirm that supplemental oxygen and room air flow are off and determine the current continuous monitoring status (SpO₂, electrocardiographic, neither, both). Inspired by ecological momentary assessment,²⁷ this observational approach is the most feasible method to determine true continuous monitoring status across a wide range of hospitals with varying chart documentation and physiologic monitor data infrastructures. These in person observations are necessary even if monitor orders exist because the presence of orders for continuous SpO₂ monitoring are poorly predictive of actual monitoring status (data from current 56-hospital study led by same team conducting this study). Sites will transmit data using REDCap, a secure research data management tool.²⁸ At the conclusion of the intervention period, questionnaires will be electronically distributed to hospital staff on each participating unit.

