- Are any pulse oximetry measurements documented in the chart since the patient has been off respiratory support (e.g. supplemental oxygen or room air flow)?
- Do they have an active continuous pulse oximetry monitoring order in the chart right now?
- Do they have an active continuous electrocardiographic/cardiorespiratory monitoring order in the chart right now?
- For hospitals with integration of medical device data into electronic health records:
 - Is there at least 1 pulse oximetry data point visible in the chart from the same minute that rounds occurred?
 - Is there at least 1 pulse oximetry data point visible in the chart for each of the 15 minutes preceding when rounds occurred?
 - Is there at least 1 pulse oximetry data point visible in the chart for each of the 15 minutes following when rounds occurred?

5.2.3 The following data elements will be abstracted from the chart and stored in the individual site's separate master list alongside the coded ID, admission date, and data collection rounds date but NOT entered into the study database and NOT transmitted outside of the institution where the patient is hospitalized:

- Patient first name
- Patient last name
- Patient medical record number
- Patient admission /account number (a hospital-specific identifier in the EHR that identifies the specific admission)

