5.3 Bedside visual observation “rounds”

- Date and time rounds occurred at this patient’s bedside (the exact time, to the minute, using the time displayed on the bedside monitor as the time of record)
- Based on observing the patient at the bedside, are they currently receiving any respiratory support (e.g. supplemental oxygen or nasal cannula flow)?
- Are they being continuously pulse oximetry monitored right now based on bedside observation?
- Are they being continuously electrocardiographically/cardiorespiratory monitored (using chest leads to measure heart rate, heart rhythm, and/or respiratory rate) right now based on bedside observation?
- Field notes based on brief real time inquiry of health care professionals, if performed, regarding why the patient is continuously monitored

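### Nothing requires a unit's bedside observations to be finished before staff are asked why a child is monitored, so the question could modestly lower later observations in the same round

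*Combined protocol and SAP*

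**What the plan says.** Section 4.2 assigns the measurement to the people who deliver the intervention: "Implementation teams will conduct data collection rounds and supplemental chart review", "targeting data collection at least twice per week in order to acquire sufficient data for audit and feedback intervention". It then allows an optional question to staff. The condition is "If any hospital staff responsible for the care of the patient are present and available on the unit", and the permission is that "the data collector may perform real-time inquiry if feasible, briefly asking about the indications for monitoring individual patients".

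Section 5.1 describes the round as bed to bed: "They will then walk to the bedside of each eligible infant with bronchiolitis". It gives the purpose as to "determine true continuous monitoring status". Section 5.3 lists the bedside items. The last of them, after the monitoring-status items, is "Field notes based on brief real time inquiry of health care professionals, if performed, regarding why the patient is continuously monitored".

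For hospitals with device integration, Section 5.2.2 adds three chart items: the minute of the round, the 15 minutes before it, and the 15 minutes after it. The third reads "Is there at least 1 pulse oximetry data point visible in the chart for each of the 15 minutes following when rounds occurred". Section 2.2 makes the bedside finding the gold standard. Section 6.3.3 does not say which of the three items defines a positive.

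The use rate is a secondary endpoint (6.2), calculated within each hospital (6.3.2). The same data feed the weekly dashboard, and local use rates guide how much further education a site gives (4.2).

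**The concern.** A question about why a child is monitored, put by a member of the team promoting less monitoring, may act as a prompt. If it comes partway through a unit, children seen afterwards on that unit are observed under a condition that the earlier ones were not. The question depends on staff being available and on feasibility, so exposure would differ by site, unit and shift. It would not be a constant that cancels when units or hospitals are compared.

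Three things could be touched: the use-rate endpoint, the unit and hospital comparisons fed back each week, and, at device-integration hospitals, agreement on the post-round item. On the last, suppose a child is correctly recorded as monitored, staff are then asked why, and monitoring stops within the next 15 minutes. The chart item becomes negative against a correct bedside positive. Because the question concerns monitored children, such disagreements would fall on bedside positives and lower apparent sensitivity, although the feed worked as intended.

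**Working it through.** **Order of events.** The plan gives no figure on this point, so the first check is to set the sections together. Section 4.2 permits the question and sets no order. Section 5.1 has the collector going from bed to bed. Section 5.3 puts the question last among the items for each child. None of them defers the question to the end of the unit, and none places it before the other children are seen. Observing one child, asking that child's nurse, and moving to the next bed therefore complies with the protocol. So does observing everyone first.

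**What is exposed.**

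- The questioned child's own bedside status: most naturally already recorded, because the question comes last on the form and presupposes monitoring.
- That child's same-minute and preceding-15-minute chart items: not affected by a later question.
- That child's following-15-minute item: exposed.
- Children seen later on the same unit: exposed.

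**Possible size for the use rate (illustration).**

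Inputs from the documents:

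- Base use rate 46% (1.2.5).
- At most 300 unique patients per hospital and an average of 5 units per hospital (3.3.2).
- Intervention period of 2-4 months (3.3), with rounds targeted at least twice a week (4.2).

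Inputs assumed:

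- One observation per patient.
- Monitoring statuses independent between children.
- Every monitored child prompts a question.
- A chance p of 5-10% that a child who would have been found monitored is off the monitor when observed, because of an earlier question on that unit.

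Step 1, rounds per hospital. At 52/12 = 4.33 weeks per month and two rounds a week, 2 months gives 2 × 4.33 × 2 ≈ 17 rounds and 4 months gives 4 × 4.33 × 2 ≈ 35.

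Step 2, children per unit per round, n. 300/(5 × 35) = 1.7 and 300/(5 × 17) = 3.5.

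Step 3, share f of observations made after a question on the same unit and round. The k-th child is exposed if at least one of the previous k−1 was monitored, which has probability 1 − 0.54^(k−1). Averaging over k = 1 to n gives

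f = 1 − (1 − 0.54^n)/(0.46 n).

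- n = 1.7: 0.54^1.7 = 0.351, so f = 1 − 0.649/0.782 = 0.17.
- n = 3.5: 0.54^3.5 = 0.116, so f = 1 − 0.884/1.61 = 0.45.

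Non-integer n is an interpolation.

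Step 4, shift. Observed rate = 46% × (1 − f p), so the shift in points is 46 × f × p.

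| f | p = 5% | p = 10% |
|---|---|---|
| 0.17 | 0.4 | 0.8 |
| 0.45 | 1.0 | 2.1 |

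The range is therefore about 0.4 to 2 points downward. It would be smaller where questions are skipped or patients are fewer, and larger with repeat observations of the same child or at a hospital with higher use than 46%.

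**Device data.** The documents give no basis for a number here. The conclusion is conditional: it matters only if the following-window item is used to classify monitoring, which Section 6.3.3 leaves open.

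**The case against.** The strongest reply is that the plan's only fault here is silence. A reader might infer that the protocol has staff questioned before other children are observed. It does not say so, and the form's item order suggests that the questioned child's status is recorded first. A reader might also infer that staff have only just been educated when the question comes. Outreach is delivered before the intervention period and afterwards at a frequency the site PI sets (4.1, 4.2), so that is not supported either.

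The mechanism is also a chain. A brief question about one child has to lead staff to take another child off the monitor before the collector reaches that bed. The documents offer no evidence that this happens. A child who has been taken off is truly unmonitored when seen, so the momentary status is still recorded correctly.

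The consequence is limited as well. The endpoint is secondary and descriptive, the study is a single-arm feasibility pilot with questionnaire scores as its primary endpoint, and no between-hospital test is planned. Section 3.1 already accepts tailored delivery and concurrent quality-improvement work, both of which make hospitals differ. Bedside time to the minute and per-patient field notes give a partial trace of which observations followed a question.

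Most of this stands and keeps the point small. It does not remove it. The stated aim of the rounds is the true status, and a status changed by the round itself is not the one that would otherwise have been found. No field for whether or when inquiry took place is listed, so affected observations cannot be separated reliably afterwards. The inquiry may be meant as part of the strategy, but the documents do not say so, and its timing would still need recording.

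**Conclusion.** The point holds as a modest gap in the measurement procedure. The protocol permits inquiry within the round and does not protect later observations on the unit, or the questioned child's following window, from it. The use rate could be lowered by roughly 0.4 to 2 points from 46% where inquiry is made. That rests on the protocol's counts, the assumptions listed in the working, and a 5-10% chance of a status change that no document supplies.

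A reader might be tempted by a larger figure. A shift of about 7 points arises with f = 0.8 and p = 20%: 46% × (1 − 0.16) = 38.6%. But f = 0.8 needs about 11 children per unit per round (1 − 0.999/5.06 = 0.80), against the 1.7 to 3.5 implied by the protocol's own counts, and nothing in the documents supports p = 20%. Nor do they support saying that the question does lower the rate; it could.

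The effect on device validation is real in principle but conditional on which chart item is used. It does not touch the same-minute or preceding-window items of the questioned child.

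**What to change.** In Sections 4.2 and 5.3, state that monitoring status is recorded and time-stamped for all eligible patients on a unit before any inquiry is made on that unit. Where the COVID-19 accommodation in 5.3.1 means asking the nurse about respiratory support, record monitoring status first. Add a form field for whether inquiry took place and at what time.

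In Section 6.3.3, base the test characteristics on the same-minute and preceding-window items, or flag following-window data that overlap an inquiry. A compulsory 15-minute wait is not recommended: across about five units per hospital it would mean waiting or return visits at every round, and the flag deals with the problem in the analysis.

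The cost is two sentences, the added inquiry field and a line in the analysis section. The collector goes back to staff at the end of the unit, so a few inquiries may be lost; they are already optional.

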4.3 At conclusion of the intervention period

- Administer questionnaire-based psychometrically valid measures to hospital staff assessing feasibility, acceptability, appropriateness,²⁶ and perceived safety of the audit and feedback strategy.

5 STUDY EVALUATIONS AND MEASUREMENTS

5.1 Overview

Data collection will be operationalized at sites during periodic in-person observational "rounds" during the intervention period. During a data collection round, site investigators will first identify all

patients currently admitted to their hospital's non-ICU pediatric wards with bronchiolitis by reviewing the census of each unit that cares for children with bronchiolitis and examining the charts of patients meeting age criteria to determine if they are eligible. They will then walk to the bedside of each eligible infant with bronchiolitis to confirm that supplemental oxygen and room air flow are off and determine the current continuous monitoring status (SpO₂, electrocardiographic, neither, both). Inspired by ecological momentary assessment,²⁷ this observational approach is the most feasible method to determine true continuous monitoring status across a wide range of hospitals with varying chart documentation and physiologic monitor data infrastructures. These in person observations are necessary even if monitor orders exist because the presence of orders for continuous SpO₂ monitoring are poorly predictive of actual monitoring status (data from current 56-hospital study led by same team conducting this study). Sites will transmit data using REDCap, a secure research data management tool.²⁸ At the conclusion of the intervention period, questionnaires will be electronically distributed to hospital staff on each participating unit.

5.2 Chart review

5.2.1 Site investigators will provide the following contextual information about audit and feedback and educational outreach delivery events, using a framework previously described:²⁹

- Date of event
- What type of session was held? (audit data review, educational outreach session, email, webinar, etc)
- Who was the audience (role composition, (e.g. nurses and residents from the 3 East unit)
- What information was delivered?
- Were specific behavior changes in response to the data discussed?
- Were structural changes discussed?
- Were other changes discussed?
- Were comparison data discussed?
 - The same hospital's past season performance
 - Other hospitals' past season performance
 - Other hospitals' current season performance
 - Performance of other units in the same hospital during current season
 - Performance of other units in other hospitals during current season
- Were graphs presented?
- How fresh were the most recent data discussed? (e.g. from the previous week)
- Implementation dates and details of any active quality improvement projects occurring concurrently

5.2.2 The following data elements will be abstracted from the chart and stored in the study database:

- Hospital
- Admission date and time
- Coded patient-admission ID – this is an identifier for each unique patient-admission to allow the data analysis to account for clustering of observations within individual patient-admissions. This is not an actual patient identifier assigned by the hospital; it is a study-specific coded identifier with the linkage master list document held by the individual site (no

actual patient identifiers other than the dates listed here are transmitted to CHOP from other sites).

- Unit name
- Bed number
- Patient age
- Patient sex
- Patient race and ethnicity
- Patient primary diagnosis and chronic conditions
- Forms of chronic neurologic impairment (e.g. static encephalopathy, cerebral palsy, hydrocephalus, spina bifida, epilepsy/seizure disorder, hypotonia, other form of neurologic impairment)
- Technology dependence (e.g. short-term feeding tube, long-term feeding tube, central venous line, renal dialysis)
- History of apnea or cyanosis during this illness
- History of ICU stay earlier in this admission
- Patient gestational age
- How long have they been off respiratory support (e.g. supplemental oxygen or room air flow), according to the chart?
- Are any pulse oximetry measurements documented in the chart since the patient has been off respiratory support (e.g. supplemental oxygen or room air flow)?
- Do they have an active continuous pulse oximetry monitoring order in the chart right now?
- Do they have an active continuous electrocardiographic/cardiorespiratory monitoring order in the chart right now?
- For hospitals with integration of medical device data into electronic health records:
 - Is there at least 1 pulse oximetry data point visible in the chart from the same minute that rounds occurred?
 - Is there at least 1 pulse oximetry data point visible in the chart for each of the 15 minutes preceding when rounds occurred?
 - Is there at least 1 pulse oximetry data point visible in the chart for each of the 15 minutes following when rounds occurred?

5.2.3 The following data elements will be abstracted from the chart and stored in the individual site's separate master list alongside the coded ID, admission date, and data collection rounds date but NOT entered into the study database and NOT transmitted outside of the institution where the patient is hospitalized:

- Patient first name
- Patient last name
- Patient medical record number
- Patient admission /account number (a hospital-specific identifier in the EHR that identifies the specific admission)

5.3 Bedside visual observation “rounds”

- Date and time rounds occurred at this patient’s bedside (the exact time, to the minute, using the time displayed on the bedside monitor as the time of record)
- Based on observing the patient at the bedside, are they currently receiving any respiratory support (e.g. supplemental oxygen or nasal cannula flow)?
- Are they being continuously pulse oximetry monitored right now based on bedside observation?
- Are they being continuously electrocardiographically/cardiorespiratory monitored (using chest leads to measure heart rate, heart rhythm, and/or respiratory rate) right now based on bedside observation?
- Field notes based on brief real time inquiry of health care professionals, if performed, regarding why the patient is continuously monitored

5.3.1 COVID-19 related accommodations

Due to hospitals experiencing shortages of personal protective equipment such as surgical masks, and the interest in protecting the health and safety of data collection staff, we will permit the following modifications to the observational rounds for hospitals actively limiting entry into patient rooms to only essential personnel:

- The data collector may obtain the respiratory support status by asking the bedside nurse responsible for the care of the patient, so no room entry is required
- The data collector may obtain the continuous monitoring status by any of the following methods, so no room entry is required:
 - Viewing the monitor from outside the patient room (e.g. through a door)
 - Viewing the monitor from a central station
 - Viewing the monitor using an existing remote continuous monitor viewing platform used by clinicians at the hospital for patient care (e.g. AirStrip)

The method used for determining respiratory support status and continuous monitoring status will be noted in the data collection form.

